6. STATISTICAL METHODS OF ANALYSIS

6.1 General Principles

The statistical analyses will be performed by [REDACTED] with approval of the Sponsor, using SAS® Version 9.4 (or higher). All tables, figures and listings will be produced in landscape format.

In general, all data will be listed by subject and visit/time point where appropriate. The summary tables will be stratified by, or have columns corresponding to, treatment groups.

The total number of subjects in the treatment group (N) under the specified population will be displayed in the header of summary tables.

Data will be summarized using descriptive statistics for continuous variables. Unless otherwise specified, descriptive statistics will include number of subjects, mean, standard deviation, minimum, median, and maximum. Number of subjects with missing values will also be displayed, but only if non-zero. The minimum and maximum statistics will be presented to the same number of decimal places as the original data. The mean and median will be presented to one more decimal place than the original data. The standard deviation will be presented to two more decimal places than the original data.

In summary tables of categorical variables, counts and percentages will be displayed. The count [n] indicates the actual number of subjects in a particular category, which should always be less than or equal to the total number of subjects in the respective study group with known (non-missing) category [M]. Percentage will be obtained by: % = $n/M*100$. Unless otherwise specified, all percentages will be expressed to one decimal place.

All statistical tests will be two-sided at a significance level of $\alpha = 0.05$, unless otherwise indicated.

Baseline will be defined as the last assessment, scheduled or not, prior to the first dose of the study drug, unless otherwise specified. This notion of baseline will also be referred to as Part I baseline. Part II baseline will be defined as the last assessment, scheduled or not, prior to the first dose of the study drug in Part II. Part II baseline will be used in analysis of findings collected in Part II for subjects initially randomized to Placebo and re-randomized to SCD-044

(█ mg or █ mg) in Part II. Throughout this SAP, if the word “baseline” is used without qualification “Part I” or “Part II”, it will refer to Part I baseline.

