6.9 Efficacy Analyses

6.9.1 Analysis of the primary and key secondary endpoints

6.9.1.1 Primary analysis

The primary analysis will be performed on the ITT population.

Subjects in the ITT population with missing EASI at Week 16 or missing baseline will be imputed as non-responders for the primary endpoint. Similarly, subjects in the ITT population with missing vIGA at Week 16 or missing baseline will be imputed as non-responders for the key secondary endpoint.

Additionally, the subjects with intercurrent events, i.e. those who took any rescue medications (systemic or topical) prior to Week 16, took any prohibited medications prior to Week 16 (as determined by blinded data review) and discontinued the study drug prior to Week 16 will be considered non-responders for both the primary and key secondary endpoint. Subjects will be known to take systemic rescue medications prior to Week 16 if this is recorded at the “Rescue Medications” CRF or “Concomitant Medications” CRF or the subject attended any of “Systemic Rescue Medications Visits” 7 to 10. Topical rescue medications will be identified through a review of the “Concomitant Medications” CRF.

For both primary and key secondary endpoint the number and percentage of subjects achieving the endpoint will be provided. Comparisons between each active group and the placebo group will be performed pairwise. Each comparison will be done using Cochran-Mantel-Haenszel (CMH) test stratified [REDACTED]

If all strata have no subject in one of the treatment groups, a value of 0.1 will be added to all cells in the corresponding table in order to prevent dividing by 0, as suggested in Greenland and Robins (1985). The estimates of Mantel-Haenszel common risk (response rate) difference between each active dose group and placebo, along with 95% confidence interval, will be provided. The p-value from the Breslow-Day test for homogeneity of strata will also be provided. If the p-value of the Breslow-Day test is ≥ 0.05 , the treatment-by-strata interaction is not significant. In the case of heterogeneity between the strata, in-depth analysis will be conducted to understand the source of the interaction; Fisher’s exact test will be used instead of CMH.

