6.9.1.2 Sensitivity analyses

The following sensitivity analyses will be performed to explore the effects of missing data on the primary endpoint and the key secondary endpoint:

1. Analysis similar to the primary analysis on the ITT population, but with missing endpoints imputed using Last Observation Carried Forward (LOCF) approach. For this

analysis the latest available post-baseline assessment of EASI will be carried forward to impute missing Week 16 assessments. Subjects with missing baseline or no post-baseline assessment prior to Week 16 will be excluded from this analysis. Additionally for subjects with intercurrent events, i.e. those who took topical or systemic rescue medications prior to Week 16, took prohibited medications prior to Week 16 or discontinued treatment prior to Week 16 the last available post-baseline assessment obtained prior to the start of the rescue medication will be used to impute Week 16 assessment. If no post-baseline assessment obtained prior to the intercurrent event (start of rescue medication, start of prohibited medication, discontinuation of treatment) is available, such subject will be excluded from this analysis.

2. Analysis similar to the primary analysis on the ITT population, but with missing endpoints imputed using Active Treatment Worst Case (ATWC) approach. For this analysis any subjects in the Placebo group with missing response or with an intercurrent event will be imputed as responders, while any subjects in any active treatment group with missing response or with an intercurrent event will be imputed as non-responders.
3. Tipping point analysis. This analysis will consist of a series of analyses similar to the primary analysis of the primary and key secondary endpoints with varying proportions of subjects with missing endpoint value or with intercurrent events imputed as responders or non-responders. The analysis will be performed for each active treatment group vs. placebo and for each combination of X1, the percentage of subjects with missing endpoint value or with intercurrent events in the placebo group and X2, the percentage of subjects with missing endpoint value or with intercurrent events in the active group. Both X1 and X2 will range from 0% to 100% in steps of 25%.

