For each pair of (X1, X2), X1% of subjects will be randomly drawn from the subjects with missing values or intercurrent events in placebo group and X2% of subjects will be randomly drawn from the subjects with missing values or intercurrent events in the active group. These randomly selected X1% subjects in the placebo and X2% subjects in the active group will be imputed as responders. The remaining subjects with missing endpoint value or intercurrent events will be imputed as non-responders. Analysis then will be conducted using the combined observed data and imputed data for each treatment group using the CMH test as described for the primary analysis in section 6.9.1.1. The random draw procedure will be repeated 49 times for each pair of (X1, X2) and the median p-value for the active vs. placebo comparison will be used for the conclusion. The estimate of the CMH common risk (response rate) difference between the treatment groups associated with the p-value selected as median will also be shown. If the same median p-value is obtained in more than one of the 49 random draws, the largest difference will be selected. The random seed for the draw will be preset as 441916 to ensure the analysis is repeatable and amenable to validation via double programming. If one pair of X1 and X2 is found to reverse the study conclusion (i.e., median p-value > 0.05 [tipping point analysis will be performed only if the primary analysis reached p-value ≤ 0.05]), then these parameters will be the tipping points.

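### The 25% tipping-point grid can place the reversal up to almost one step too late, and fractional subject counts have no rounding rule

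*SAP*

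**What the plan says.** SAP 6.9.1.2 item 3 re-imputes subjects who have a missing endpoint or an intercurrent event. X1 is the percentage of such placebo subjects counted as responders, and X2 is the same for the active arm. The grid is fixed: "Both X1 and X2 will range from 0% to 100% in steps of 25" per cent. Coverage is complete: "The analysis will be performed for each active treatment group vs. placebo and for each combination of X1" and X2, which gives 5 × 5 = 25 pairs per comparison.

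At each pair the subjects to be made responders are drawn at random: "The random draw procedure will be repeated 49 times for each pair of (X1, X2"). The median p-value is used, and the matching risk difference is shown too: "The estimate of the CMH common risk (response rate) difference between the treatment groups associated with the p-value selected as median will also be shown".

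The naming rule is: "If one pair of X1 and X2 is found to reverse the study conclusion (i.e., median p-value > 0.05"), "then these parameters will be the tipping points". The visible text describes no search between grid points and no rounding rule for a percentage that is not a whole number of subjects. Protocol 9.8 leaves the full tipping-point method to the SAP.

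**The concern.** A tipping point answers a simple question: how many unfavourable outcomes among the unobserved ones would remove significance? The SAP answers it only at 0, 25, 50, 75 and 100% of the pool, and the grid pair itself is what it calls the tipping point. If the reversal falls between two grid values, the label goes to the later one. The error has one direction, and it makes the result look sturdier.

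The pool need not be small. Under SAP 6.9.1.1 it takes in any topical or systemic rescue, prohibited medication or treatment discontinuation before Week 16, as well as missing data. With 18 to 30 placebo subjects in the pool, one step is 4.5 to 7.5 subjects. That is too coarse to separate a result that 2 subjects overturn from one that needs 7. The missing rounding rule adds a second problem: two programmers could follow the same text and report different tipping points, although the SAP presets the seed so that double programming will agree.

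**Working it through.** **Inputs from the documents.** Total about 240 (Protocol 4.1); allocation 3:1:1:3 (SAP 3.1). Arm sizes are 240 × 3/8 = 90 for placebo and high dose, and 240 × 1/8 = 30 for each of the other doses. Test: "Each comparison will be done using Cochran-Mantel-Haenszel (CMH) test stratified" by factors that are redacted. Tests are two-sided at 0.05 (SAP 6.1).

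**Assumptions.** The visible text gives no response rates and no pool size. I assumed 10–20% placebo response, active minus placebo of 15–35 points, and a placebo pool of 4, 9, 18 or 27 of 90 (5–30%), plus worked examples with pools up to 30. The test is treated as one stratum, so p depends only on counts and the 49 draws change nothing. The plan states no tipping point, so there is no figure to reproduce.

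**Formula.** With a active and b placebo responders, m = a + b and N = n₁ + n₂: χ² = (a − n₁m/N)² / [n₁n₂m(N − m) / (N²(N − 1))], on 1 df, without continuity correction. Start at X1 = X2 = 0 (everyone in the pool a non-responder), then switch j placebo subjects to responder.

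**Worked case: 30/90 v 14/90, 30 placebo subjects re-imputed**
- j = 0: m = 44, χ² = 8²/8.358 = 7.658, p = 0.006.
- j = 4: m = 48, χ² = 6²/8.849 = 4.068, p = 0.044.
- j = 5: m = 49, χ² = 5.5²/8.965 = 3.374, p = 0.066. **The reversal is here: 5/30 = 16.7%.**
- Grid point X1 = 25%: 7.5 subjects, rounded half up to 8; m = 52, χ² = 4²/9.296 = 1.721, p = 0.190. **This is the tipping point that the grid gives.**

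**Further cases (90 v 90, X2 = 0, half-up rounding)**

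| Responders, active v placebo | Pool | p at (0, 0) | One-subject reversal | First reversing grid point | Lag |
|---|---|---|---|---|---|
| 30 v 14 | 30 | 0.006 | 5 (16.7%) | 25% (8) | 3 |
| 36 v 14 | 30 | 0.0003 | 10 (33.3%) | 50% (15) | 5 |
| 27 v 14 | 27 | 0.021 | 2 (7.4%) | 25% (7) | 5 |
| 36 v 14 | 18 | 0.0003 | 10 (55.6%) | 75% (14) | 4 |

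In the last row a 10% grid would give 60% (11 subjects, p = 0.084), and a 5% grid would give 55% (10 subjects, p = 0.0585), which is the exact count.

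**How often.** Of 112 assumed scenarios significant at (0, 0), 75 reverse somewhere along X2 = 0 and 37 never do. In the 75, the grid names a later subject count in 49 and the same count in 26. The lag averages 1.8 subjects (7.8 percentage points). The largest is 7 − 1 = 6 subjects, or 25 − 3.7 = 21.3 points (1 of 27 reported as 25%, in a 30 v 90 comparison).

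**Upper limit.** Over every significant 90 v 90 table with 0 to 90 − k placebo responders, where k is the pool size, the largest lag is 4 subjects for k = 20 (step 5), 6 for k = 25 (step 6.25) and 7 for k = 30 (step 7.5). The limits are the same whether counts are rounded up, down or half up. With k = 4 a step is exactly one subject and the lag is 0.

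**Rounding.** Take 30/90 v 14/90 with 18 re-imputed; 25% is 4.5 subjects.
- Rounded down to 4: p = 0.044, still significant, so the first reversing grid value is 50% (9 subjects, p = 0.254).
- Rounded up to 5: p = 0.066, so it is 25%.

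**The case against.** The best defence is that all 25 pairs are analysed and the risk difference is shown as well, so the last significant pair and the next one bracket the true boundary. With 36/90 v 14/90 and 30 re-imputed, p is 0.026 at 25% and 0.279 at 50%, and a careful reader sees that the reversal lies between. That stands if the output shows the whole grid; the shells are in a separate document (SAP 9). It does not fully answer the point, because the SAP attaches the label to the reversing pair and not to the bracket, and a bracket 5 to 8 subjects wide is a coarse answer.

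Three stronger inferences are tempting, and the documents do not support them.
- A reader might infer that the true reversal always comes earlier than the one reported. It does not: the counts coincided in 26 of the 75 reversing scenarios, and with a small pool the grid is already complete.
- A reader might infer that only the first reversing pair will be reported, so that overstatement is certain. The SAP does not say first; its wording lets any reversing pair qualify.
- A reader might infer that a fragile result could pass as unbreakable. The corner X1 = 100%, X2 = 0% is on the grid and is also the active-treatment-worst-case analysis (item 2). Coarse and one-subject searches agreed on whether a reversal exists in all 112 scenarios. The corner must be read with the sign of the risk difference: in the first worked case it is 30/90 v 44/90, p = 0.034 in favour of placebo.

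The SAP also does not rank this analysis above the other two sensitivity analyses, and it ties no decision rule to it. Finally, the real test is stratified, so the exact integers here illustrate the effect and are not what the plan would output.

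**Conclusion.** The point holds as one of limited resolution plus a missing rounding rule. Counted in subjects along X2 = 0, the reported tipping point is the same as the true one or later, by less than one step. For 90 v 90 with 20 to 30 placebo subjects re-imputed, that is at most 4 to 7 subjects. The size rests on assumed response rates and pool sizes, enrolment at the planned 240, and a single-stratum test in place of the redacted stratification. The primary test, the testing hierarchy and the question whether any reversal exists are not affected. This is a cheap improvement to a sensitivity analysis and does not correct an invalid one.

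**What to change.** In SAP 6.9.1.2 item 3, replace the 25% steps by every whole number of imputed responders in each arm, from 0 to the number re-imputed in that arm. If percentages are preferred, use steps of at most 5% and state how fractional counts are rounded. Keep the CMH test, the 49 draws, the median p-value and the preset seed. Report the whole boundary between significant and non-significant pairs, as subject counts and as the resulting response rates in each arm.

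The cost is computing time and a larger output. With 30 subjects re-imputed in each arm there would be 31 × 31 = 961 pairs, or 961 × 49 = 47,089 tests per comparison and endpoint, against 25 × 49 = 1,225 now. A 5% grid needs 21 × 21 = 441 pairs, or 21,609 tests. Either is a light load, and a heat map shows the result on one page.

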6.9.1.3 Supplementary analyses

The following supplementary analyses will be performed:

1. Analysis similar to the primary analysis, but on the Per Protocol population using observed cases only with no imputations.
2. Analysis similar to the primary analysis, but on the ITT population excluding the subjects with protocol deviations related to the COVID-19 pandemic. This analysis will be performed only if more than 5% of subjects have protocol deviations related to the COVID-19 pandemic.

6.9.1.4 Subgroup analyses

The primary analysis of the primary and key secondary endpoints will also be repeated by subgroups:

In case when subgrouping variable was used as the stratification factor for the primary analysis, this variable will not be used as a stratification variable for the analysis of this subgroup.

The Breslow-Day test will be performed for each subgrouping variables in order to verify the homogeneity of endpoints. In the case of sparse data Fisher's exact test will be used instead of CMH.

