4. STUDY POPULATION

4.1 Number of Subjects

Approximately 240 subjects will be enrolled in the study in a [REDACTED] the following treatment groups:

- Placebo of SCD-044 product [REDACTED]
- SCD-044 Tablets (Low dose)
- SCD-044 Tablets (Intermediate dose)
- SCD-044 Tablets (High dose)

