3. STUDY OVERVIEW

3.1 Study Design

Subjects in this randomized, double-blind, placebo controlled, parallel-group, multiple-center study will be assigned to treatment with the investigational products or placebo control according to a randomization scheme and [REDACTED] schedule.

- **Part I** (16 weeks): Subjects will be randomized to Placebo, Low dose ([REDACTED] mg), Intermediate dose ([REDACTED] mg) or High dose ([REDACTED] mg) of SCD-044 in 3:1:1:3 ratio

[REDACTED] to assess primary and secondary endpoints at 16 weeks.

- [REDACTED]
- [REDACTED]

Statistical Analysis Plan
Study Code SCD-044-19-16

Version Final

Date Jan 21, 2025

- [REDACTED]
- [REDACTED]
- [REDACTED]

Phone or in person contacts may be scheduled for visits [REDACTED] visits to collect information on concomitant medication, compliance with the study drug use, health changes (AEs & AESI), queries for PML and PRES and to provide instructions.

[REDACTED]

[REDACTED]

[REDACTED]

Subjects will be admitted into the study after informed consent has been obtained. An Unscheduled Visit is allowed at any time, for any reason, if in the Investigator's opinion it is warranted. If a Subject is discontinued from the study during an Unscheduled Visit, the Unscheduled Visit will be referred to as an Early Discontinuation Visit and all procedures scheduled for Early Discontinuation will be performed. If the Unscheduled Visit is not an Early Discontinuation Visit (i.e., the Subject will continue to take part in the study), then all procedures scheduled for that Unscheduled Visit will be performed. Subjects who are discontinued early from the study must attend the Follow-up visit 4 weeks after the date of Early Discontinuation.

If necessary due to the COVID-19 pandemic, Visit 18 may have assessments done at home or remote visit. Remote visits must be discussed and consulted with the CRO's and the Sponsor's medical monitor before planning. Scheduled blood collection (for these visits only) may be waived if the individual subjects have not had a clinically significant changes or undesired trend in lab or chemistry values prior to visit 15. Remote assessments or delayed visit 18 will be recorded in the source documents and noted as a minor protocol deviation.

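### SAP 6.9.1.4 asks a Breslow-Day test to verify subgroup homogeneity, which a non-significant result cannot do with arms of about 90 and 30 subjects; show the between-subgroup difference in response-rate differences with its 95% CI instead

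*SAP*

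**What the plan says.** SAP 6.9.1.4 plans subgroup analyses of both main endpoints: "The primary analysis of the primary and key secondary endpoints will also be repeated by subgroups". It then gives the purpose of the accompanying test: "The Breslow-Day test will be performed for each subgrouping variables in order to verify the homogeneity of endpoints". The section sets no threshold for that test, no equivalence margin and no action that follows from the result.

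The only visible reading of a Breslow-Day p-value is in SAP 6.9.1.1, where it concerns the strata of the primary analysis: "If the p-value of the Breslow-Day test is ≥ 0.05 , the treatment-by-strata interaction is not significant". The general level is in SAP 6.1: "All statistical tests will be two-sided at a significance level of" 0.05.

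For the comparisons themselves, SAP 6.9.1.1 says "Comparisons between each active group and the placebo group will be performed pairwise", and it plans Mantel-Haenszel risk differences with 95% confidence intervals. The estimand tables in SAP 2.2 and 2.4 name the difference in proportions as the summary measure. Sample size and allocation are in Protocol 4.1 ("Approximately 240 subjects will be enrolled in the study") and SAP 3.1 ("of SCD-044 in 3:1:1:3 ratio", in the order placebo, low, intermediate, high).

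**The concern.** Homogeneity is an equivalence-type conclusion. Supporting it needs an estimate of how far the effect differs between subgroups and an interval narrow enough to exclude differences that matter. The visible text of 6.9.1.4 offers a test of the opposite kind, whose null hypothesis is homogeneity, and describes its purpose as verification. When such a test has little power, a non-significant result says almost nothing.

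There is also a mismatch of scale. Breslow-Day tests whether odds ratios are equal, but the estimands are differences in proportions. Equal odds ratios can go with quite different risk differences when the placebo rate varies between subgroups.

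At stake is a sentence in the report. This is a Phase IIb dose-ranging trial, and whether the effect is consistent across patient types bears on whom the next study should enrol. The stated purpose invites a claim of consistency that the data could not support.

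**Working it through.** **Inputs from the documents.** N is about 240 (Protocol 4.1). Allocation is 3:1:1:3 (SAP 3.1). Comparisons are pairwise against placebo (SAP 6.9.1.1). Alpha is 0.05, two-sided (SAP 6.1). Missing outcomes count as non-response in the ITT population, so dropout does not shrink the arms.

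**Inputs assumed, because they are not visible.** Placebo response is 15% in both subgroups. There are two subgroups, split 25:75, 50:50 or 75:25. The active arm gains 20, 30, 40 or 50 points over placebo in one subgroup and nothing in the other. The threshold p ≥ 0.05 is borrowed from SAP 6.9.1.1 and 6.1.

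The documents show no power figure for this test, so there is none to reproduce.

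**Step 1, arm sizes.** 240 × 3/8 = 90 and 240 × 1/8 = 30. The high-dose comparison is 90 v 90. Each lower dose is 30 v 90. At 25:75, the smaller subgroup of a 30-subject arm has 7 or 8 people.

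**Step 2, how often a complete loss of effect is missed.** Trials were simulated with binomial responses, 20,000 to 40,000 per scenario in the main runs. The Breslow-Day statistic was computed against the Mantel-Haenszel common odds ratio (1 degree of freedom, no Tarone correction). The miss rate is the share of trials with p ≥ 0.05. Repeat runs agree to within about one point.

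| Effect in the subgroup that keeps it | 90 v 90 | 30 v 90 |
|---|---|---|
| 20 points (35% v 15%) | about 70–76% | about 81–87% |
| 30 points (45% v 15%) | about 48–60% | about 67–77% |
| 40 points (55% v 15%) | about 29–43% | about 52–64% |
| 50 points (65% v 15%) | about 14–29% | about 35–50% |

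Each range covers the three splits; the lowest figure is at, or within simulation error of, the even split. Under a common odds ratio the test rejected in 5.1% (90 v 90) and 5.3% (30 v 90) of trials, so it is calibrated but weak.

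The placebo rate matters less than the effect size. For a 30-point effect at 50:50, the miss rate is 47% and 67% with placebo at 10%, and 49% and 69% with placebo at 25%. Over a wider grid (placebo 5–25%, effects of 15–50 points, 20–80% of subjects in the subgroup that keeps the effect), it runs from about 15% to 83% at 90 v 90 and from 36% to 94% at 30 v 90.

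**Step 3, precision of the quantity of interest.** The 95% CI half-width for the between-subgroup difference in risk differences is 1.96 × √(sum of the four p(1−p)/n terms). For 45% v 15% in one subgroup and 15% v 15% in the other:

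- 90 v 90, 50:50: 1.96 × √(0.2475/45 + 3 × 0.1275/45) = 1.96 × √0.0140 = 23.2 points.
- 30 v 90, 50:50: 1.96 × √(0.2475/15 + 0.1275/15 + 2 × 0.1275/45) = 1.96 × √0.0307 = 34.3 points.
- 25:75 with the effect in the smaller subgroup: about 28 points (22 and 68 per arm), and about 41 points (8 and 22 active, 22 and 68 placebo).

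So an observed between-subgroup difference of zero would still leave true differences of roughly 23–28 points (high dose) or 34–41 points (lower doses) unexcluded.

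**Step 4, scale.** Going from 15% to 45% is an odds ratio of (0.45/0.55)/(0.15/0.85) = 4.64. Apply the same odds ratio to a subgroup with 5% placebo response: odds 0.0526 × 4.64 = 0.244, a response of 0.244/1.244 = 19.6%. The risk differences are 30 and 14.6 points, yet Breslow-Day has nothing to detect. Even a high-powered, non-significant result would not show homogeneity of the SAP's own effect measure.

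**The case against.** The strongest reply is that 6.9.1.4 contains no decision rule. It sets no threshold and requires no statement in the report, and its verb can be read as checking. The 0.05 wording in 6.9.1.1 concerns the strata of the primary analysis, and it calls the interaction not significant, which is accurate. That stands. A reader might infer that the SAP will declare homogeneity whenever p ≥ 0.05, but no sentence says so. The point therefore concerns the stated purpose.

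Second, repeating the primary analysis by subgroup already yields risk differences with 95% CIs. In the 30-point scenario, among trials where Breslow-Day is non-significant, the interval for the no-effect subgroup includes zero in about 94–96% (90 v 90) and 98–99% (30 v 90). A reader of the tables would see that. This limits the harm, but two separate intervals do not give the between-subgroup contrast.

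Third, the miss rate is not a property of the plan. A reader might take about half (high dose) and about 70% (lower doses) as the general result; those figures belong to a 30-point effect with a near-even split. With a 50-point effect the high-dose rate can fall to about 14%. Nor are the data usually compatible with no effect in some subgroup. If the effect is truly 45% v 15% in both, then among trials with p ≥ 0.05 at least one subgroup interval includes zero in only about 17% at 90 v 90 (50:50), though about 66% at 30 v 90.

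Finally, low-powered interaction tests are usual in Phase II, and these analyses sit outside the hierarchical testing in 6.9.1.1. Both are true, and they set the weight of the point.

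**Conclusion.** The concern holds as a wording and presentation point on an exploratory analysis. A non-significant Breslow-Day result cannot verify homogeneity at the implied arm sizes, and it addresses odds ratios while the estimands are differences in proportions.

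The size depends on assumptions the documents do not supply, so Step 2 should be read as a range. The qualitative conclusion is firmer than any single figure: the test is weaker for the 30-subject doses throughout, and even for the high dose it is reasonably sensitive only if the lost effect is very large.

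A reader might infer that the main efficacy conclusions are at risk. They are not: no primary or key secondary conclusion depends on the test in 6.9.1.4. The subgroup list is not visible in the public text, and nothing here criticises that. This is a cheap improvement, not a defect in the trial's main inference.

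**What to change.** In SAP 6.9.1.4, replace the clause giving the purpose of the Breslow-Day test with:

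> as an exploratory, low-powered check for heterogeneity. For each subgrouping variable and each active dose versus placebo, the between-subgroup difference in the response-rate difference will be presented with its 95% CI for EASI-75 and vIGA response at Week 16. A p-value ≥ 0.05 will not be taken as evidence of homogeneity.

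Present the high-dose comparison first, because the 30-subject arms carry little information.

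The added quantity follows from output already planned. The estimate is the difference between the two subgroup risk differences, and its standard error is the square root of the sum of their squared standard errors. For a variable with more than two levels, name a reference level.

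The cost is a wording change and one extra column in the subgroup tables. No new data or subjects are needed, and the primary test is unchanged. The downside is that the intervals will be wide and will show that homogeneity cannot be claimed.
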